### 3 **Section A: Experimental Design**

4 This study will employ a quasi-experimental design utilizing repeated measures (specific  
5 aim 1), followed by cross-sectional analysis (specific aims 2 and 3). The target sample size for  
6 the study will be 25 physical therapists and 90 patients. Patient-reported outcome measures were  
7 selected based upon their reliability, validity and internationally accepted use. Given that there is  
8 no single universal patient reported outcome measure for the shoulder, multiple measures will be  
9 utilized during the third aim of this project.

#### 10 Specific Aim 1

11 The first specific aim will be to determine the reliability of the shoulder symptom  
12 irritability classification scale. To address this aim, the project will analyze paired rater  
13 judgments of shoulder symptom irritability (high, moderate or low) from 90 patients with  
14 shoulder pain. Raters will be physical therapists from multiple clinics trained in rating shoulder  
15 symptom irritability. Prevalence-adjusted, bias-adjusted Kappa for ordinal scales (PABAK-OS)  
16 will be the primary measure of reliability. However, analysis may be adjusted based on the data  
17 distribution.

#### 18 Specific Aim 2

19 The second aim is to compare level of functional limitation between shoulder symptom  
20 irritability groups. To address this aim, the project will analyze patient-reported functional  
21 measures using analysis of variance with post-hoc analysis to compare functional disability  
22 across different levels of shoulder symptom irritability. The independent variable will be the  
23 shoulder symptom irritability level, and dependent variables will include patient-reported  
24 functional status measures. The hypothesis is that patients with higher irritability will report  
25 greater functional deficits.

#### 26 Specific Aim 3

27 The final specific aim is to determine if the level of shoulder symptom irritability dictates  
28 the chosen intervention intensity. To address this aim, raters will select planned intervention  
29 choices for each of the 90 patients, utilizing a pre-specified list of possible physical therapy  
30 interventions. Data analysis will include PABAK-OS for correlation, and independent t-test for  
31 differences between clinical specialist and non-specialist groups. The hypothesis is that patients  

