32 with high irritability will be prescribed interventions aimed at minimizing the physical stress to  
33 the affected tissue(s), while patients with low irritability will be prescribed interventions at a  
34 higher intensity to address the physical impairments.

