#### 143 Procedures

144 At least 2 raters will be recruited from each site. Raters will be trained with the following  
145 materials: (1) Collaborative Institutional Training Initiative (CITI) training for those involved in  
146 consenting the patients; (2) the reading of the Staged Approach for Rehabilitation Classification:  
147 Shoulder Disorders with direction to pay special attention to the section on Level 3  
148 classification and Table 3;6(pp 795-6) and (3) a short online narrated presentation to reinforce  
149 understanding of the content. The intent of this training method is to increase the generalizability  
150 of the study results, and to avoid overly specialized training methods that would be difficult to  
151 reproduce clinically.

152        Patients will be recruited by the raters from their regular caseload (Appendix C). Patients  
153 will receive a brief explanation about the study, provide informed consent, and be asked to  
154 complete the functional questionnaires as part of the outpatient admissions process. The first  
155 therapist will rate the patient's shoulder symptom irritability level during the normal examination  
156 process utilizing the intake (Appendix C). Raters will inquire on the presence of night or resting  
157 pain and complete a physical examination including measurement of active and passive shoulder  
158 flexion. Range of motion measurements will be utilized for direct comparison and to determine  
159 the onset of pain during passive motion. Shoulder flexion will be measured utilizing goniometric  
160 procedures described elsewhere. Active range of motion testing will be performed in  
161 standing and passive range of motion testing will be performed in supine.

162        After the first rater has completed their examination and prior to any intervention that  
163 may change the shoulder symptom irritability, a second rater, blinded from the first rater's  
164 assessment, will then examine and rate the subject (Appendix C). In addition to the shoulder  
165 symptom irritability rating, both raters will also be asked to provide a treatment intensity  
166 recommendation based upon the examination findings (Appendix C). Data collection forms will  
167 be placed in a sealed envelope and sent via interoffice mail for analysis. To maintain rater  
168 blinding, raters will be asked to not discuss ratings until data collection is complete.

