#### 172 ***Section D: Statistical Analysis***

173        Descriptive statistics will be used to characterize both raters and patients. Frequencies  
174 will be utilized for categorical variables, and means with standard deviations for continuous  
175 variables.

176        A repeated measures design, utilizing two raters per subject, will be utilized to determine  
177 inter-rater reliability. The raters will independently rate the subject's shoulder symptom  
178 irritability level utilizing the recently developed shoulder symptom irritability scale. The inter-  
179 rater reliability will be evaluated using the PABAK-OS statistic. For evaluation of statistical  
180 significance, a two-tailed confidence interval will be utilized with  $\alpha$  set to 0.05, and the null  
181 hypothesis will be that the PABAK-OS will be  $<0.40$ .

182        Analysis of variance with post-hoc analysis will be utilized for evaluation of differences  
183 in patient reported functional limitation and pain subscales between shoulder symptom  
184 irritability groups. For evaluation of statistical significance,  $\alpha$  will be set to 0.05.

185        Lastly, to evaluate correlation between intervention intensity and diagnosed level of  
186 shoulder symptom irritability, the PABAK-OS statistic will be used. Additionally, independent t-  
187 tests will be utilized to evaluate for difference between groups for hypotheses 1 and 2 of aim 3.  
188 For evaluation of statistical significance,  $\alpha$  will be set to 0.05.

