**189      Section E: Limitations and Potential Problems**

190      One potential problem is the need to have more than one clinician trained and available to  
191      rate the subjects at all times. Many clinics in this regional hospital network have fewer than  
192      three physical therapists and thus, there will be a risk of potential subject loss during the  
193      reliability phase. I intend to address this barrier via incentives derived from grant application  
194      and via administrative support as the hospital network has a defined educational and research  
195      vision.

196      A limitation to this study is the use of physical therapists and consecutive patients from a  
197      single regional hospital network. However, the regional hospital network encompasses over 30  
198      locations with over 80 physical therapists, 18 of which are clinical specialists. Furthermore, the  
199      need to have more than one clinician trained and available to rate the subjects at all times could  
200      potentially lead to subject loss during the reliability phase.

201      Another limitation of this study would be the limitation of data in aim 3 to only those  
202      subjects who had complete agreement between raters. This would potentially reduce the power  
203      of this part of the study. However, the risk to internal validity by utilizing the subjects without  
204      complete agreement would be a greater threat to the study than the limitation of power to aim 3  
205      and, to minimize the effect of this limitation, sample size will be twice the size needed to power  
206      the study at 80%.

207      Additionally, the FOTO functional status instrument is a proprietary measure, and while  
208      it is utilized nationally and internationally, it is not likely that it will be universally used due to  
209      its proprietary nature, thus limiting the generalizability of that aspect of the study. Finally, the  
210      data obtained regarding clinician outcome trends is retrospective rather than prospective. While  
211      longitudinal data would be ideal, the aim of utilizing retrospective data is to determine if further  
212      investigation utilizing longitudinal data is necessary, given the time and financial implications of  
213      such a study.

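### The Aim 3 specialist versus non-specialist t-test treats correlated choices as independent if run on individual choices, so it need not hold its 5% level; a model with rater and patient effects should replace it.

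*Combined protocol and SAP*

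**What the plan says.** Section A, Specific Aim 3, plans an independent t-test for "differences between clinical specialist and non-specialist groups". Section D repeats the plan as t-"tests will be utilized to evaluate for difference between groups for hypotheses 1 and 2 of aim 3", with alpha 0.05. The document contains no numbered Aim 3 hypotheses. The only one stated is that patients "with high irritability will be prescribed interventions aimed at minimizing the physical stress to" the affected tissue, with higher intensity for low irritability. Specialists do not appear in it.

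Section A describes the data as "choices for each of the 90 patients, utilizing a pre-specified list of possible physical therapy" interventions. Section C, Procedures, says that "both raters will also be asked to provide a treatment intensity" recommendation, and that "At least 2 raters will be recruited from each site". Section B expects 25 raters and 90 patients. Section E notes "Many clinics in this regional hospital network have fewer than" three therapists, and puts the network at over 30 "locations with over 80 physical therapists, 18 of which are clinical specialists". It also restricts the Aim 3 data to patients on whom the raters fully agreed.

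Appendix C holds one three-level treatment-strategy question and a separate list of six treatments. It records rater certifications (OCS, SCS, FAAOMPT, Other), but no section says which of these make a rater a specialist.

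**The concern.** An independent t-test assumes that every observation is independent of the others. Here the grouping variable is a property of the rater, and each rater contributes several choices. If therapists have stable habits in how hard they treat, choices by one rater resemble each other. A chance difference between a few raters can then pass for a specialist effect. Each patient is also judged twice, so the two choices share whatever that patient brings. Depending on whether the two raters are of opposite or the same type, this sharing makes the t-test too cautious or too liberal.

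At stake is whether a reported specialist difference, or its absence, can be read at the stated 5%. No section mentions clustering or pairing for this comparison. Because the unit is not stated and the hypotheses referred to are absent, different analyses would fit the text.

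**Working it through.** **The plan's own figure.** The only sample-size figure is 48 for the Aim 1 kappa (0.80 against a null of 0.40, 80% power). For two raters and a binary rating with prevalence p, let q = p(1-p) and d = [q(0.80-0.40)]². Then n = (1.960+0.842)² / [d/(p²+0.4q) + 2d/(0.6q) + d/((1-p)²+0.4q)]. With p = 0.30 (assumed; the document gives none), q = 0.21 and d = 0.00706. The sum is 0.0406 + 0.1120 + 0.0123 = 0.1648, and n = 7.849/0.1648 = 47.6, so 48. Prevalence 0.50 gives 41.2 and 0.20 gives 60.1. This figure concerns Aim 1 only. The specialist comparison has no power basis.

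**Inputs.** From the documents: 25 raters, 90 patients, two raters per patient, pairing within site, alpha 0.05. Assumed: two-sided testing; 80 patients left after the agreement restriction; 25 raters in 12 clinics (11 of two, one of three); rater variance share r from 0 to 0.20; patient share 0.4; and 6 specialists (18/80 × 25 = 5.6) or 12.

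**Hand check.** Choices per rater: m = 80 × 2/25 = 6.4. Ignoring unequal loads, the true variance of the difference between groups, relative to what the t-test assumes, is about

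F = 1 + (m-1)r + c,

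where c = -0.4 if every pair is one specialist and one non-specialist (the patient effect cancels), c = +0.4 if both raters are always of the same type, and c is about 0 if specialists are spread at random. The type I error is about 2[1 - Φ(1.96/√F)].

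| Rater share | Mixed pairs: F, error | Random: F, error | Same-type: F, error |
|---|---|---|---|
| 0 | 0.60, 1.1% | 1.00, 5.0% | 1.40, 9.8% |
| 0.05 | 0.87, 3.6% | 1.27, 8.2% | 1.67, 12.9% |
| 0.10 | 1.14, 6.6% | 1.54, 11.4% | 1.94, 15.9% |
| 0.20 | 1.68, 13.0% | 2.08, 17.4% | 2.48, 21.3% |

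**Simulation, t-test on choices, 80 patients, patient share 0.4** (rater share 0, 0.05, 0.10, 0.20; 2,000 runs per cell, standard error √(0.2 × 0.8/2,000) = 0.9 points at 20%):

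- Six specialists placed at random: 5.5%, 10.0%, 12.4%, 19.3%.
- One specialist per clinic: 1.1%, 4.5%, 8.2%, 15.8%.
- Same-type pairs: about 10% rising to about 25%.

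**Simulation, all 90 patients kept, patient share 0.5** (same rater shares; 1,500 runs per cell):

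| Pairing | t-test on choices | t-test on rater means |
|---|---|---|
| Random, 6 specialists | 5.5, 8.7, 11.9, 18.1% | 5.6, 5.9, 4.6, 3.9% |
| One specialist per clinic | 1.1, 2.5, 7.0, 14.8% | 1.1, 1.2, 2.6, 3.5% |
| Same-type, 6 specialists | 11.1, 15.6, 19.3, 26.1% | 11.5, 9.4, 9.0, 8.1% |

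A three-level outcome behaved the same way: 0.8% to 17.4% under correlation, 5.5% with none. At patient share 0.4, the t-test on rater means gave about 2-3% with mostly mixed and 7-9% with mostly same-type pairs.

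**Modelling both effects.** Generalised least squares with rater and patient effects, variances taken as known, gave 3.6% to 5.7% in all 32 continuous scenarios, same-type pairs included. A linear mixed model with estimated variances and (raters - 2) degrees of freedom gave 3.1-6.1% with random placement, 3.0-5.9% with about half the pairs mixed, and 2.5-6.4% with nearly all or all mixed. It was not run on same-type pairs.

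**Precision.** Ignoring patient correlation, a rater mean has variance r + (1-r)/6.4 in units of a single choice. The part that depends on the number of choices, (1-r)/6.4, is 0.148/0.198 = 75% of this at r = 0.05, 0.141/0.241 = 58% at 0.10 and 0.125/0.325 = 38% at 0.20. Both the number of raters and the choices per rater matter.

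**The case against.** The plan never says that the choice is the unit. If the t-test is meant per rater and specialists fall at random across clinics, it comes close to 5%. That is fair, and it is why the point is conditional. It does not settle the matter, because rater means still miss 5% when pairs are mostly mixed or mostly same-type, and the plan fixes neither unit nor pairing.

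It can also be said that the outcome is less open than it looks. Procedures asks for a treatment intensity recommendation, and the single three-level strategy question fits that well. This largely stands, so the weight here is on the test and not on the choice of form. A site effect may also exist, and neither the simulations nor the proposed model include one.

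Three stronger readings are tempting. A reader might infer that the error is inflated in every case. It is not: mixed pairs with little rater variance bring it below 5%. A reader might infer that precision depends on the number of raters alone. The variance split contradicts that. A reader might infer that only large differences are detectable. With 25 raters, 80% power on rater means needs 1.17 SD (12 v 13) to 1.60 SD (4 v 21) of rater means. At rater share 0.05 one such SD is √0.198 = 0.45 SD of a single choice, which gives 0.52-0.71. At 0.20 it is √0.325 = 0.57, which gives 0.67-0.91.

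Finally, this is an additional test within the third aim of a reliability study. That limits its importance, but it is still a planned test at 0.05.

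**Conclusion.** The concern holds in conditional form. If run on individual choices, the planned independent t-test ignores rater and patient correlation and need not hold 5%. Under the stated assumptions its error runs from about 1% (mixed pairs, no rater variance), through 9-20% (random placement, rater share 0.05-0.20), to 10-25% (same-type pairs). A t-test on one value per rater is closer, but gives about 2-3% or 7-9% at the two extremes of pairing.

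The direction and size rest on variance shares, clinic layout, specialist numbers and agreement, none of which the documents give. That the observations are not independent follows from the design itself. The missing numbered hypotheses and specialist definition are plain from the text, but alone would be matters of detail. A reader might extend the criticism to the Aim 1 reliability analysis; nothing in this point affects it.

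**What to change.** In Section D, replace the Aim 3 independent t-test with a mixed model:

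- **Outcome:** the treatment-strategy choice scored 1 to 3, or its match with the agreed irritability level; name one.
- **Model:** specialist status as fixed effect, rater and patient as random effects, small-sample degrees of freedom based on the number of raters (for example, contributing raters minus 2), two-sided alpha 0.05.
- **Report:** the difference with its 95% confidence interval, raters per group and choices per rater.

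Keep a t-test on rater means only if pairs turn out neither mostly mixed nor mostly same-type. State that precision depends on both the number of raters and the choices per rater, and that the doubled patient sample alone does not secure it. In the same edit, list Aim 3 hypotheses 1 and 2 in Section A and name the certifications that define a specialist.

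The cost is a few sentences. Certifications and choices are already on the Appendix C forms. The downside is a wider interval when raters differ. An ordinal or logistic mixed model is possible, but its error rate was not checked here.

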**189      Section E: Limitations and Potential Problems**

190      One potential problem is the need to have more than one clinician trained and available to  
191      rate the subjects at all times. Many clinics in this regional hospital network have fewer than  
192      three physical therapists and thus, there will be a risk of potential subject loss during the  
193      reliability phase. I intend to address this barrier via incentives derived from grant application  
194      and via administrative support as the hospital network has a defined educational and research  
195      vision.

196      A limitation to this study is the use of physical therapists and consecutive patients from a  
197      single regional hospital network. However, the regional hospital network encompasses over 30  
198      locations with over 80 physical therapists, 18 of which are clinical specialists. Furthermore, the  
199      need to have more than one clinician trained and available to rate the subjects at all times could  
200      potentially lead to subject loss during the reliability phase.

201      Another limitation of this study would be the limitation of data in aim 3 to only those  
202      subjects who had complete agreement between raters. This would potentially reduce the power  
203      of this part of the study. However, the risk to internal validity by utilizing the subjects without  
204      complete agreement would be a greater threat to the study than the limitation of power to aim 3  
205      and, to minimize the effect of this limitation, sample size will be twice the size needed to power  
206      the study at 80%.

207      Additionally, the FOTO functional status instrument is a proprietary measure, and while  
208      it is utilized nationally and internationally, it is not likely that it will be universally used due to  
209      its proprietary nature, thus limiting the generalizability of that aspect of the study. Finally, the  
210      data obtained regarding clinician outcome trends is retrospective rather than prospective. While  
211      longitudinal data would be ideal, the aim of utilizing retrospective data is to determine if further  
212      investigation utilizing longitudinal data is necessary, given the time and financial implications of  
213      such a study.

## APPENDIX C: SURVEYS AND DATA COLLECTION FORMS

Subject # \_\_\_\_\_

### Rater Information

Name: \_\_\_\_\_

Age: \_\_\_\_\_

Years of Practice: \_\_\_\_\_

#### Advanced Certifications Held:

- OCS
- SCS
- FAAOMPT
- Other \_\_\_\_\_

Gender:  Male  Female

#### Entry Level Degree:

- BS
- MS
- DPT

#### Highest Earned Degree:

- BS
- MS
- DPT
- PhD, ScD, EdD

For Office Use Only:  
Subject # \_\_\_\_\_

Inclusion Criteria

- 18 years old or older
- Chief complaint of shoulder pain

Exclusion Criteria

- Pain or symptoms distal to the elbow
- History of ipsilateral shoulder surgery
- Active or passive cervical spine ROM reproduces shoulder pain
- Positive Spurling's test
- Not literate in the English language
- Unable to complete the self-report functional questionnaires

- Subject meets BOTH inclusion criteria AND does not meet ANY of the exclusion criteria
- Subject does NOT meet inclusion criteria OR meets one of the exclusion criteria

PENN/ASES SHOULDER SCORE								
Subject #								
Dominant Hand:			Gender:			Affected Arm:		
L	R	Both	M	F	(circle one)	L	R	Both
PENN SHOULDER SCORE								
Part I: Pain & Satisfaction: Please circle the number closest to your level of pain or satisfaction								
How bad is your pain today?								
0	1	2	3	4	5	6	7	8
No								
Pain								
								10
								Worst
								Pain Possible
ASES Pain _____ (10 - # circled + ___ x 5 = ___)								
Pain at rest with your arm by your side:								
0	1	2	3	4	5	6	7	8
No								
Pain								
								10
								Worst
								Pain Possible
ASES Pain _____ (10 - # circled + ___ x 5 = ___)								
Pain with normal activities (eating, dressing, bathing):								
0	1	2	3	4	5	6	7	8
No								
Pain								
								10
								Worst
								Pain Possible
ASES Pain _____ (10 - # circled + ___ x 5 = ___)								
Pain with strenuous activities (reaching, lifting, pushing, pulling, throwing):								
0	1	2	3	4	5	6	7	8
No								
Pain								
								10
								Worst
								Pain Possible
ASES Pain _____ (10 - # circled + ___ x 5 = ___)								
PAIN SCORE: = ___ /30								
How satisfied are you with the current level of function of your shoulder?								
0	1	2	3	4	5	6	7	8
Not								
Satisfied								
								10
								Very
								Satisfied
ASES Satisfaction _____ (# circled)								

PLEASE TURN OVER TO COMPLETE  
QUESTIONNAIRE

---

OFFICE USE ONLY

Today's Date: / /		
	PENN SHOULDER SCORE (PSS)	ASES SHOULDER SCORE (ASES)
Pain	/30	/50
Satisfaction	/10	
Function	/60	/50
TOTAL	/100	/100

© 1998 Brian G. Leggin

\*\*The author grants unrestricted use of this questionnaire for patient care and clinical research purposes.

PENN SHOULDER SCORE/ASES SHOULDER SCORE Part II: Function: Please circle the number that best describes the level of difficulty you might have performing each activity.		No difficulty	Some difficulty	Much difficulty	Can't do at all	Did not do before injury
1. Reach the small of your back to tuck in your shirt with your hand.	3	2	1	0	X	
2. Wash the middle of your back/hook bra. (ASES #3)	3	2	1	0	X	
3. Perform necessary toileting activities. (ASES #4)	3	2	1	0	X	
4. Wash the back of opposite shoulder.	3	2	1	0	X	
5. Comb hair. (ASES #5)	3	2	1	0	X	
6. Place hand behind head with elbow held straight out to the side.	3	2	1	0	X	
7. Dress self (Including put on coat and pull shirt over head. (ASES #1)	3	2	1	0	X	
8. Sleep on affected side. (ASES #2)	3	2	1	0	X	
9. Open a door with affected side.	3	2	1	0	X	
10. Carry a bag of groceries with affected arm.	3	2	1	0	X	
11. Carry a briefcase/small suitcase with affected arm.	3	2	1	0	X	
12. Place a soup can (1-2 lbs.) on a shelf at shoulder level without bending elbow.	3	2	1	0	X	
13. Place a one gallon container (8-10 lbs.) on a shelf at Shoulder level without bending elbow.	3	2	1	0	X	
14. Reach a shelf above your head without bending your elbow. (ASES #6)	3	2	1	0	X	
15. Place a soup can (1-2 lbs.) on a shelf overhead without bending your elbow.	3	2	1	0	X	
16. Place a one gallon container (8-10 lbs.) on a shelf Overhead without bending your elbow. (ASES #7)	3	2	1	0	X	
17. Perform usual sport/hobby. (ASES #8)	3	2	1	0	X	
18. Perform household chores (cleaning, laundry, cooking).	3	2	1	0	X	
19. Throw overhand/swim/overhead racquet sports. (circle all that apply to you) (ASES #8)	3	2	1	0	X	
20. Work full-time at your regular job. (ASES #10)	3	2	1	0	X	
SCORING: (office use only)	PSS	PSS	PSS	PSS	PSS	
PSS Total of all columns = _____ (a)	_____	_____	_____	_____	_____	
Number of "X's" x 3 = _____ (b), 80 - _____ (b) = _____ (c)	_____	_____	_____	_____	_____	
(If no "X's" are circled, function score = total of columns)	ASES	ASES	ASES	ASES		
PSS Function Score = _____(a) + _____(c) = _____ x 80 = _____ of 80	_____	_____	_____	_____		
ASES Score = _____						
Total of shaded columns: _____ x 5/3 = _____ of 60						

[figure not shown]
Physical Therapy at St. Lukes - Physical Therapy at St. Luke's - West End  
INTAKE FUNCTIONAL STATUS SUMMARY

Patient:	Risk-Adjustment Criteria			
ID#:			Gender:	
Date of Birth:			Comorbidities:	
Initial DOS:			Payer:	
Body Part:		Severity:		
Impairment:		Age:		
Surgery Type:		Acuity:		
Surgery Date:				

Functional Status Measures:	Intake Score	Interpretation of FS Scores/Stages Value
Patient's Physical FS Primary Measure		Patient's Intake functional measure is out of (higher number = greater function). This FS measure places the patient in Stage 4 and means the patient has good shoulder function.
Risk Adjusted Statistical FOTO*		Given the patient's risk-adjustment variables, like-patients nationally had a FS score of 52, Stage 3, at Intake.

MCII = Points of change that is important to the patient)

MDC = Represents the smallest threshold to identify points of change that is greater than measurement error)

Rehabilitation Resource Predictor*	Predicted Value	Interpretation of Predicted Value
Points of Physical FS Change		
Discharge FS Score		Given this patient's risk-adjustment variables, and the actual Intake FS score, FOTO predicts this patient will experience at least an increase in function of 6 points (to 73 or higher), putting them in the Stage 4 level or higher at discharge.
Visits per Episode		Stage: 1 Exceedingly limited shoulder Stage: 2 Poor shoulder Stage: 3 Fair shoulder Stage: 4 Good shoulder Stage: 6 Excellent shoulder
Duration of Episodes in Days		
Satisfaction Score		

\* The above predictions are calculated for  
 1) patients who have previously utilized rehabilitation services from FOTO's national aggregate database and  
 2) using sophisticated analyses to risk adjust for the impact of ten important variables known to influence outcomes including Care type, Body Part/Impairment, Severity, Age, Acuity, Gender, Surgery, Payer, and Comorbidities.

